Treatment Cycle 2: A second treatment cycle will be allowed for subjects who did not achieve sufficient clinical improvement (e.g. VSS remains ≥ 3) on the randomized treatment (Cycle 1) as evaluated at the TOC visit or at the FU EOT+14 visits. A second treatment cycle will also be allowed for subjects with clinical cure/improvement/success who experience a recurrence before the last FU visit. During Cycle 2, subjects may receive additional treatment with ibrexafungerp for a period up to 14 days as recommended by the investigator and following discussion with the sponsor.

It is recommended that study drug be administered with or immediately after a meal or snack.

STUDY BLINDING, RANDOMIZATION, AND STRATIFICATION: This is an open-label study. Subjects will be randomized to treatment, stratified by group based on the *Candida* species and presence or absence of underlying medical conditions.

STUDY EVALUATIONS

Efficacy Evaluations

Clinical Evaluation: The signs (edema, erythema, and excoriation or fissures) and symptoms (itching, burning, and irritation) of infection will be assessed by the investigator and the subject, respectively, on the VSS Scale. The VSS Scale is a standardized, predefined scale where each sign and symptom will be given a numerical rating based on severity (absent = 0; mild = 1; moderate = 2; or severe = 3) to calculate a total composite score.

Mycological Evaluations: Mycological tests will include direct WET Mount microscopic examination (performed locally) to visualize clue cells indicative of bacterial vaginosis or trichomonas, direct microscopic examination with 10% KOH (performed locally) to identify yeast, and fungal cultures (performed at the central lab) for species identification and antifungal susceptibility testing.

Safety and Tolerability Assessments

Safety Evaluations: Safety will be evaluated throughout the study, from consent through the TOC visit, including the following parameters: AEs, concomitant medications, vital signs, safety laboratory tests, and study treatment discontinuations.

STATISTICAL ANALYSES:

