11.1. Inclusion Criteria

Subjects must fulfill all of the following criteria to be eligible for study admission:

- 1) Subject is a post menarchal female ≥ 18 years of age at the time of signing the ICF.
- 2) Subject has a diagnosis of symptomatic VVC that meets the following criteria at the Screening visit:
 - a) Minimum composite vulvovaginal signs and symptoms score of ≥ 4 with at least 2 signs or symptoms having a score of 2 (moderate) or greater on the VSS scale at baseline.
 - b) Positive microscopic examination with 10% KOH in a vaginal sample collected at Screening revealing yeast forms (hyphae/pseudohyphae) or budding yeasts
 - c) Normal vaginal pH (≤ 4.5).
 - d) Has no other vaginal co-infections based on WET Mount microscopic examination (and/or DNA probe).
- 3) Subject should also have:
 - a) A VVC with persistent symptoms despite fluconazole therapy (last dose of fluconazole must have been administered at least 7 days prior, but no longer than 28 days prior to screening).

OR

b) A recurrent vulvovaginal candidiasis (RVVC) episode with breakthrough symptoms while receiving maintenance antifungal therapy.

OR

c) A VVC episode caused by a non-*albicans candida species* known to have either intrinsic resistance to fluconazole e.g. *C.krusei* or suspected resistance to fluconazole, e.g. *C.glabrata*, *C auris* but likely without MIC data in hand.

OR

d) A VVC episode caused by *candida* species with documented resistance to fluconazole based on MIC determination.

OR

e) A known history of azole allergy or intolerance.

4) Subject is able to take oral tablets.

5) Subject is not pregnant or lactating and plans not to become pregnant. Women of childbearing potential < 1 year post-menopausal must agree to and comply with using one barrier method (male condom, female condom, and diaphragm) plus one other highly effective method of birth control, or sexual abstinence, from the time of consent through 10 days after the completion of study therapy. **Subjects must refrain from using any topical vaginal contraceptives as these may have an impact on the signs and symptoms of VVC.**

Note: Women of childbearing potential must have a negative urine pregnancy test prior to enrollment (performed by the site's local laboratory).

6) Subject is able to understand and sign a written ICF, which must be obtained prior to treatment and any study-related procedures.

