14.3. Inclusion and Exclusion Criteria

All inclusion and exclusion criteria will be reviewed at Screening (-2 \pm 1) and at Baseline (Day 1) to ensure that the subject qualifies for the trial. Screening and Baseline can be on the same day, if applicable.

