14.6. Urine Pregnancy Test

A urine pregnancy test based on the measurement of human chorionic gonadotropin with a sensitivity of at least 25 international units per liter will be performed at Screening and at unscheduled visits, if needed, by the local laboratory for all subjects of childbearing potential. The pregnancy test results will be reviewed at Baseline (Day 1) before administration of study drug.

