14.11. Rating of Vulvovaginal Signs by the Investigator Using the VSS Scale

The investigator (or qualified designee) will perform vulvovaginal examinations to rate the subject's signs of infection at the Screening, TOC and first FU visits at 14 days after EOT. The vulvovaginal examination will be repeated at the rest of the FU visits only if the subject presents with symptoms. Otherwise, no additional vulvovaginal examination will be conducted, or signs rated. Vulvovaginal examinations may be conducted at unscheduled visits, if needed.

If the subject experiences persistence or worsening or recurrence of symptoms that per the investigator's assessment (e.g. symptoms ≥ 4) warrant the use of rescue antifungal therapy, the subject may be enrolled into Treatment Cycle 2 and receive additional treatment with ibrexafungerp for a period up to 14 days as recommended by the investigator and following discussion with the sponsor.

Whether or not a subject enters Treatment Cycle 2, or be prescribed rescue therapy, a vaginal examination with rating of signs by the investigator should be completed prior to initiation of rescue therapy. If the investigator's rating of the vulvovaginal signs is not possible prior to the initiation of the rescue therapy, it should still be completed as soon as possible after rescue therapy is initiated.

Investigators will assess the signs of infection using the VSS Scale provided in Section 21 [Appendix 2]), a standardized, predefined scale where each sign of the vagina and/or vulva will be given a numerical rating based on severity, as follows:

- Edema: absent = 0; mild = 1; moderate = 2; severe = 3
- Erythema: absent = 0; mild = 1; moderate = 2; severe = 3
- Excoriation or fissures: absent = 0; mild = 1; moderate = 2; severe = 3

Other findings will be recorded using the most relevant medical term in the abbreviated physical examination page of the eCRF.

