15. STUDY SCHEDULE

Detailed schedules of all study visits and procedures are presented in Schedule of Visits and Procedures ([Table 1](#)).

The actual visits will be dependent on the Dosing Group i.e there may be overlapping visits.

Subjects entering Treatment Cycle 2, will follow the same Schedule of Visits and Procedures, starting with Baseline visit and may have visits that are Not Applicable during Treatment Cycle 1.

Table 1: Schedule of Visits and Procedures (Study SCY-078-307b)

Visit	V1 Screening ^a	V2 Baseline ^a	At Home	V3 TOC	V4 FU	V5 FU	V6 FU	V7 FU	Unscheduled Visits ^b
Day (allowable window)	Day -2(±1)	Day 1	Days 2-7	14 ±3 days post Baseline	14 ±3 days post EOT	30±4 days post Baseline	30 ±4 days post EOT	60 ±4 days post EOT	
Study Procedures									
Informed consent	X								
Enrollment and assignment of Subject ID number	X								
Inclusion/exclusion criteria ^c	X	X							
Medical history and demographics	X								
Abbreviated physical exam	X			X					If needed
Vital Signs ^k	X	X		X					If needed
Urine pregnancy test ^c	X			X					If needed
Safety laboratory blood tests ^d	X			X					If needed

Visit	V1 Screening ^a	V2 Baseline ^a	At Home	V3 TOC	V4 FU	V5 FU	V6 FU	V7 FU	Unscheduled Visits ^b
Day (allowable window)	Day -2(±1)	Day 1	Days 2-7	14 ±3 days post Baseline	14 ±3 days post EOT	30±4 days post Baseline	30 ±4 days post EOT	60 ±4 days post EOT	
Rating of vulvovaginal symptoms by the Subject^e	X	X	X	X	X	X	X	X	If needed
Vaginal Examination and rating of vulvovaginal signs by the Investigator^e	X			X	X	If symptoms	If symptoms	If symptoms	If needed
Vulvovaginal sample for other pathogens^e	X			If needed	If needed	if needed	If needed	If needed	If needed
Vulvovaginal sample for KOH and pH^e	X			If symptoms	If symptoms	If symptoms	If symptoms	If symptoms	If needed
Vulvovaginal sample for fungal culture^e	X			X	X	If symptoms	If symptoms	If Symptoms	If needed
Quality of Life Questionnaire		X		X	X	X	X	X	
Study drug dosing		X	X						
Study drug container(s) collection and subject data reviewed				X					
Phone Contact^h			X						
Prior and concomitant medication reviewⁱ	X	X	X	X	X	X	X	X	X
AE monitoring^j	X-----X				X	X	X	X	X

Abbreviations: AE = adverse event; D = day; TOC = test of cure; V = visit; FU = follow up

- a) Screening and Baseline may occur on the same day.
- b) Unscheduled visits can occur if the investigator determines there is a need for one outside of the scheduled per protocol visits.

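### No pregnancy test is required before Cycle 2 dosing, so a subject re-dosed for a late recurrence may start on a TOC test nominally 16 to about 51 days old

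*Protocol*

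**What the plan says.** **Entry to Cycle 2.** For insufficient response to Cycle 1, the Protocol Synopsis places the decision "as evaluated at the TOC visit or at the FU EOT+14 visits". The Synopsis and Sections 12.1 and 14.15 add a second route: a subject who responded and then relapses before the last follow-up visit. Either route can lead to as many as 14 days of ibrexafungerp, on the investigator's recommendation after discussion with the sponsor.

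**Schedule.** Section 15: "Subjects entering Treatment Cycle 2, will follow the same Schedule of Visits and Procedures, starting with Baseline visit". In Table 1 the urine pregnancy test is marked at V1 (Screening) and V3 (TOC). It is blank at V2 (Baseline) and at V4 to V7 (follow-up), and the unscheduled column allows it where needed.

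**Other provisions on pregnancy testing.**
- Section 14.6 says the test "will be performed at Screening and at unscheduled visits, if needed, by the local laboratory", without naming TOC. It continues: "The pregnancy test results will be reviewed at Baseline (Day 1) before administration of study drug". Table 1 footnote c likewise asks for a review of results.
- Section 11.1, inclusion 5, note: "Women of childbearing potential must have a negative urine pregnancy test prior to enrollment".
- Section 14.3 has the entry criteria reviewed at Screening "and at Baseline (Day 1) to ensure that the subject qualifies for the trial".
- Sections 14.10 and 14.11 say that, on relapse or persistence, "the subject may be enrolled into Treatment Cycle 2". Section 14.10 asks for a vaginal examination, KOH and culture beforehand.
- Section 16.5 requires immediate discontinuation if a subject becomes pregnant.

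**The concern.** The protocol treats exposure in pregnancy as something to prevent: a negative test is needed before first entry, and a pregnancy ends participation. That standard is not carried over to re-dosing. Starting the second cycle at Baseline skips the Screening column, which holds the only test placed before dosing.

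The first test marked within Cycle 2 is its own TOC, nominally 14 days after the Cycle 2 Baseline. A full 14-day course has its last dosing day 13 days after that Baseline, so this test nominally comes after all the drug has been taken. The course may also be twice the longest Cycle 1 course (14 against 7 days). At stake is therefore the safety of subjects re-dosed late, not any efficacy result.

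**Working it through.** The plan gives no figure for test age, so there is none to reproduce. The check has two parts: whether any provision orders a test, and how old the last scheduled test would be.

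**1. Does any provision order a test before the Cycle 2 dose?**
- Table 1, V2 Baseline: no test marked.
- Section 14.6 and footnote c: these call for a review of results. A review can be met with an existing result, and no maximum age is set.
- Inclusion 5 note: tied to enrollment. Even if entering Cycle 2 counts as enrollment (the word used in 14.10 and 14.11), an earlier negative test satisfies it.
- Section 14.3 and the Table 1 eligibility mark at V2: these cover not being pregnant but add no test. Nor can the entry criteria be applied literally at Cycle 2, because exclusion 8 bars prior ibrexafungerp.
- Unscheduled visits: a test is permitted, not required. At the scheduled follow-up visits the cell is empty.

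None orders a new test.

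**2. Age of the TOC test at Cycle 2 entry.**

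Inputs (Sections 10.1.1 and 12.1), in days after Baseline:
- EOT = treatment days − 1 = 0, 2 or 6 for the 1-, 3- and 7-day regimens.
- TOC = 14, window 11 to 17.
- EOT+14 has a window of ±3; Baseline+30, EOT+30 and EOT+60 have ±4.

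Formula: age = entry day − TOC day. Smallest = earliest entry − 17; largest = latest entry − 11.

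| Cycle 2 entry | Entry day (1/3/7-day) | Nominal age | With windows |
|---|---|---|---|
| TOC | 14 | 0 | 0 |
| EOT+14 | 14/16/20 | 0/2/6 | 0 (visits can coincide) to 23 − 11 = 12 |
| Baseline+30 | 30 | 16 | 26 − 17 = 9 to 34 − 11 = 23 |
| EOT+30 | 30/32/36 | 16/18/22 | 26 − 17 = 9 to 40 − 11 = 29 |
| Day before EOT+60 | 59/61/65 | 45/47/51 | see below |
| EOT+60 itself | 60/62/66 | 46/48/52 | 56 − 17 = 39 to 70 − 11 = 59 |

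Recurrence must precede the last visit, so the nominal upper end is 51 days (7-day regimen). The 59 is the value at EOT+60 itself on the last permitted day; one day earlier gives 58. If the evening-then-morning option in Section 14.15 moves EOT by one day, each age based on EOT rises by one day. Any delay between finding the recurrence and the Cycle 2 Baseline adds to these ages.

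**3. Is late entry foreseen?** Baseline to EOT+60 is 60, 62 or 66 days, in line with the roughly 65 days in Section 10.3. That section doubles the duration to about 130 days with Cycle 2 (2 × 65 = 130), which fits entry near the end of follow-up.

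**The case against.** The strongest case against is that Cycle 2 is never automatic. Each re-dosing is discussed between investigator and sponsor, eligibility and pregnancy results are looked at again at Baseline, and a relapse between visits would usually prompt an unscheduled visit where a test is available. SAP Section 6.1.1 also recalculates Cycle 2 baselines for laboratory results and physical examination, which Table 1 does not mark at V2, so entry to Cycle 2 may involve more than the V2 column. The CRF might show this but is not available here. Section 14.10 concerns vaginal samples, so its silence on pregnancy testing is weak evidence.

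These points lower the realistic risk. They do not close the gap: each leaves the test to judgment, and SAP 6.1.1 does not name pregnancy testing and allows Cycle 1 values to be carried forward.

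Three stronger readings are tempting and are not supported.
- *That the last test is the Screening test, because 14.6 omits TOC.* Section 14 refers to Table 1 for the detailed schedule, Table 1 marks TOC, SAP Section 5.2 follows Protocol Section 15, and SAP Section 6.6.2 summarises the test by visit. The omission is a wording mismatch.
- *That contraception lapses between the cycles.* The duty runs "from the time of consent through 10 days after the completion of study therapy". Ending it 10 days after Cycle 1 is one reading only: Cycle 2 drug is also study therapy, and inclusion 5 requires, with no end date, that the subject does not plan a pregnancy.
- *That every Cycle 2 entrant is affected.* Entrants at the two decision visits named in the Synopsis have a recent test.

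**Conclusion.** The point holds for late-recurrence entrants of childbearing potential. Followed as written, the plan allows them to start up to 14 days of ibrexafungerp on a TOC test nominally 16 to about 51 days old, 9 to 59 with visit windows. For entry at TOC or EOT+14 the test is 0 to 12 days old, and the point has little force.

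This assumes that the TOC test in Table 1 is done and that nobody chooses to repeat it. The documents do not give the number of late entrants, which could be small or zero. They also give no data on harm in pregnancy, so the consequence cannot be sized. No efficacy endpoint or SAP analysis is affected. It is a patient-safety gap that should be closed because closing it is cheap, not evidence that pregnant subjects would knowingly be dosed.

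**What to change.** 1. Table 1, urine pregnancy test row: add an X at V2 Baseline, labelled Cycle 2 only.
2. Sections 14.6 and 12.1: require, for subjects of childbearing potential, a negative urine pregnancy test on the day of the Cycle 2 Baseline and before the first Cycle 2 dose. A TOC test done that day meets this.
3. Section 14.6: add TOC to the listed visits, to agree with Table 1.

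The test age at re-dosing then falls to 0 days. The cost is one local urine test for each Cycle 2 entrant of childbearing potential without a TOC test that day (mainly the late entrants), at a visit already planned, plus a short protocol amendment. The contraception wording needs no change for this purpose: the same-day test protects whichever way that clause is read.

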10.1.1.5. FU visit (14 \pm 3 days after EOT)

At this visit, study drug container(s) will be returned, reviewed, and treatment compliance evaluated. The investigators and the subjects will again rate the signs and symptoms of infection on the VSS Scale and the subjects will complete a QOL questionnaire.

Vulvovaginal samples for fungal culture, species identification, and antifungal susceptibility testing will be obtained and sent to a designated central laboratory. Additional vaginal samples will be obtained for a KOH and vaginal pH testing by the local laboratory if symptoms persist or have worsened. AEs and/or concomitant medications will be evaluated.

10.1.1.6. FU visits 30 (\pm 4) days after Baseline, 30 (\pm 4) days after EOT and 60 (\pm 4) days after EOT:

At the FU visits, subjects will rate their symptoms of infection on the VSS Scale and will complete a QOL questionnaire. Only if VSS symptoms are present will the investigator perform a vulvovaginal examination to rate the subject's signs of infection and collect samples for pH determination, KOH testing, and fungal culture.

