- c) Results should be reviewed prior to enrollment at Baseline (Day 1).
- d) Hematology and blood chemistry. Safety laboratory tests will be performed by a qualified laboratory.
- e) A vaginal examination with rating of signs by the investigator will be completed at the TOC visit. If the subject experiences persistence or worsening or recurrence of symptoms, after the baseline visit (e.g. symptoms ≥ 4), that warrant the use of rescue antifungal therapy, the symptoms that led to the use of rescue antifungal therapy must be documented in the eCRF. Additionally, vulvovaginal samples should be obtained for KOH testing and pH measurement (both at the clinical research unit), fungal culture (central laboratory) and investigation of other pathogens such as bacterial vaginosis and *Trichomonas vaginalis* (at the local lab). If the investigator's rating of the vulvovaginal signs and vaginal samples collection are not possible prior to the initiation of the rescue therapy, they should still be completed as soon as possible after rescue therapy is initiated.
- f) Vulvovaginal examinations will be repeated at the FU visits only if the subject presents symptoms. Otherwise, no additional vulvovaginal examination will be conducted or signs rated.
- g) The first study drug dose (Day 1) will be administered at the clinical research center and the subsequent dose(s) will be self-administered by the subjects at approximately 12 ± 3 hour intervals at home.
- h) The Day 3, 5, and 7 phone contacts will be used to evaluate symptom resolution, AEs, and concomitant medications.
- i) Only the use of antifungal medications, vaginal (topical) medications, antibiotics for any reason or any other medications to treat an AE will be recorded after the TOC visit through the last study visit (FU).
- j) New AEs starting after TOC will be recorded only if they led to the use of other antifungal medications or topical vaginal treatment, if they are a vaginal bacterial or parasitic infection, or if they are deemed related to the previously administered study drug
- k) Blood pressure (systolic and diastolic), heart rate and body temperature

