5.2. Study Schedule

The scheduled assessments will be carried out as described in Section 15 of the study protocol.

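### Read literally, Table 1 footnote f withholds V4 sign rating from symptom-free subjects, against Table 1, 10.1.1.5 and 14.11: a risk to secondary endpoints, mainly in Group B

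*Protocol*

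**What the plan says.** Footnote f to Table 1 (Protocol Section 15) reads "Vulvovaginal examinations will be repeated at the FU visits only if the subject presents symptoms" and continues "Otherwise, no additional vulvovaginal examination will be conducted or signs rated". Table 1 labels the visit 14 days after EOT as V4 FU, so the footnote's words cover it.

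Other places treat V4 differently:

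- **Table 1**, row "Vaginal Examination and rating of vulvovaginal signs by the Investigator": X at V1, V3 (TOC) and V4; conditional on symptoms only at V5, V6 and V7.
- **Protocol 10.1.1.5** (V4): "The investigators and the subjects will again rate the signs and symptoms of infection on the VSS Scale", with no condition. The synopsis says the same.
- **Protocol 10.1.1.6** (V5-V7): "Only if VSS symptoms are present will the investigator perform a vulvovaginal examination".
- **Protocol 14.11**: the investigator examines "to rate the subject's signs of infection at the Screening, TOC and first FU visits at 14 days after EOT". The symptom condition that follows is confined to the remaining FU visits.
- **Footnote e**: sign rating is completed at TOC. It gives no matching statement for V4.
- **SAP 5.2**: "The scheduled assessments will be carried out as described in Section 15 of the study protocol". That section holds both the Table 1 grid and footnote f.

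**The concern.** Footnote f is close to the symptom-condition sentence in 14.11, but lacks the words that restrict it to the later visits. A site working from the schedule page therefore has two instructions for V4.

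Clinical cure needs a signs-plus-symptoms total of 0. Under footnote f the symptom-free subjects, who include every possible cure, have no sign score, while every rated subject has at least one symptom and so a composite of at least 1. No rule in either document handles this. The SAP imputes nothing unless specified (6.1.2), and the treatment-failure rule in Protocol 18.4 covers a missing TOC assessment only.

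At stake are the V4 results for cure, improvement, success, cure combined with mycological response, and composite change, all named secondary endpoints. SAP 6.4.1.2 also plans a t-test of 3-day against 7-day dosing on the composite score without naming visits. If V4 is included, footnote-following sites would contribute mostly symptomatic subjects, and the loss could differ between the two randomized regimens.

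**Working it through.** The documents give no figure on this point, so there is nothing to reproduce. The check has four steps.

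**1. Who has a V4 visit separate from TOC.** Count days after Baseline (Day 1), taking EOT as Day 1, 3 or 7, that is 0, 2 or 6 days after Baseline. TOC is 14 ± 3 days after Baseline, so days 11-17. V4 is EOT + 14 ± 3.

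| Regimen | V4 window | Days shared with TOC (11-17) |
|---|---|---|
| 1 day | 11-17 | 7 |
| 3 days | 13-19 | 5 |
| 7 days | 17-23 | 1 |

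Section 15 expects overlapping visits by dosing group. A visit that serves as both V3 and V4 has signs rated under footnote e. The exposure therefore falls mainly on Group B, and most on the 7-day regimen.

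**2. Observed V4 cure, unrated subjects excluded.** Assumptions: 50% of subjects are symptom-free and all of these truly score 0; *s* is the share of subjects at sites following footnote f. In a regimen with separate visits:

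observed cure = 0.5(1 − s) / [0.5 + 0.5(1 − s)]

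- s = 25%: 0.375/0.875 = 42.9%
- s = 50%: 0.25/0.75 = 33.3%
- s = 100%: 0/0.5 = 0%

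Pooled over three equal regimens, with 1-day V4 combined with TOC and so unaffected:

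observed cure = [(1/3)(0.5) + (2/3)(0.5)(1 − s)] / [1/3 + (2/3)(1 − 0.5s)]

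- s = 25%: 0.4167/0.9167 = 45.5%
- s = 50%: 0.3333/0.8333 = 40%
- s = 100%: 0.1667/0.6667 = 25%

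The true value is 50% throughout.

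**3. Sensitivity to the cure rate.** Borrow the TOC cure rates of the two earlier Phase 3 studies in Protocol 7.1.4 (50.5% and 63.3%) as *p*, and assume that *q* = 5-15% of all subjects are symptom-free with residual signs. In a regimen with separate visits, observed cure = (1 − s)p / [1 − s(p + q)]:

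- s = 25%: 44.0-45.3% (p = 50.5%) or 57.3-59.0% (p = 63.3%)
- s = 50%: 34.9-37.5% or 48.1-52.0%
- s = 100%: 0% in both

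The pattern is the same.

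**4. If unrated signs were set to 0.** The documents give no such rule. Assume 50% are symptom-free and 10-20% of those have a residual sign, so true cure is 45% to 40%. In a regimen with separate visits:

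overstatement = s × 0.5 × (0.10 to 0.20)

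- s = 25%: 1.25-2.5 points
- s = 50%: 2.5-5 points
- s = 100%: 5-10 points

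**The case against.** The strongest reply is that a table footnote governs the cells to which it is attached, and the attachment of footnote f cannot be seen. In the text available, the sign row carries only the marker e. No marker f appears anywhere in the table. If f sits on the three conditional cells, V5-V7, it does not conflict with the grid. This stands as a limit on the finding. It does not settle the scope the other way: the marker g is also missing, although footnote g plainly concerns study drug dosing, so the markers may simply have been lost in conversion. The wording of f still names the FU visits without exception.

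Second, the intended design is clear. The grid, the synopsis, 10.1.1.5 and 14.11 all call for V4 sign rating, and Table 1 and 14.10 also schedule a culture sample from every subject at that visit. A site would have to let one footnote override all of these. This stands too, and it makes widespread loss unlikely. A reader might infer that the protocol forbids V4 sign rating in symptom-free subjects; taken as a whole, it does not.

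Third, the study is exploratory and not powered for formal comparisons. That limits the weight of the point, but does not remove a contradiction that leaves a named endpoint without a score.

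**Conclusion.** Footnote f is wrong as written, with consequences for secondary endpoints only. Read literally, it conflicts with Table 1, 10.1.1.5 and 14.11, although its intended scope cannot be confirmed. Where a site follows it at a separate V4 visit, observed V4 cure at that site is 0% by construction. Across the trial the effect depends on how many sites do so, which the documents cannot tell us. The shares of 25%, 50% and 100%, the 50% cure rate and the residual-sign rates are all assumptions.

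Three stronger readings are tempting and not supported:

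- That the primary endpoint is at risk. Footnote e secures sign rating at TOC.
- That 42.9%, 33.3% or 0% describes the whole trial. These figures hold only within a regimen whose V4 and TOC visits are separate; pooled with a combined 1-day visit they become about 45.5%, 40% and 25%.
- That scoring unrated signs as 0 overstates cure by 5-10 points in general. That needs every site to follow the footnote.

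At V5-V7 sign rating is conditional by design. How cure is scored there is a separate question that this correction does not answer.

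**What to change.** Reconcile footnote f with Table 1, 10.1.1.5 and 14.11:

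1. Word footnote f so that the symptom condition applies only to the remaining FU visits, V5, V6 and V7, as 14.11 already does.
2. Extend footnote e's statement on sign rating from TOC to TOC and V4.
3. In the SAP, flag V4 records without sign ratings, tabulate them by site and regimen, and state that they are not scored as 0.

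The cost is a footnote correction, a memo to sites and a short SAP addition. No procedure is added, because Table 1 already schedules the V4 examination for everyone. If enrolment is already under way or complete, item 3 remains useful: it shows which sites followed which instruction.
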